### 8.9.1. Liquid Meal (for MMTT)

A liquid meal consisting of approximately 700 kcal (**16 fluid ounces**) of Ensure Plus® (Vanilla) will be administered to the participants as listed in the [SoA](#). The liquid meal will be **consumed within approximately 10 minutes** on all MMTT days.

### 8.9.2. Plasma Glucose, Plasma Insulin, C-Peptide, Glucagon and HbA1c

At each timepoint specified in the [SoA](#), a sufficient amount of blood will be collected for analysis of plasma glucose, plasma insulin, C-peptide, glucagon, and HbA1c for MMTT.

The timing of blood samples for assessment of  $AUC_{(0-4)}$  as part of the MMTT will be based on the start time of the liquid meal such that the sample for the 15-minute time point is collected approximately 5 minutes after completion of the liquid meal.

Where triplicate FPI is to be measured, the 3 samples should be collected approximately 5 minutes apart. FPI and FPG values will be used to calculate HOMA-IR (see [Section 9.3.4](#)).

### **8.9.3. Body Weight**

Body weight measurements will be obtained at the time points outlined in the [SoA](#). If possible, the same scale should be used for a particular participant for all body weight measurements obtained at the CRU. For measuring weight, a scale with appropriate range and resolution is used and must be placed on a stable, flat surface.

Body weight will be measured at outpatient visits to the study site as listed in the [SoA](#) under the following conditions:

- After void of urine;
- After removal of shoes, bulky layers of clothing, and jackets so that only light clothing remains;
- While remaining still during measurement.

During admission to the CRU, body weight will be measured at the time points listed in the [SoA](#). Measurement will be taken under the following conditions:

- In the morning, prior to eating and drinking and prior to dose administration, where applicable;
- After the participant has been asked to void;
- While wearing only a hospital gown and no shoes;
- While remaining still during measurement.

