**Table 1. Overall Visit Schedule and List of Procedures (use with Table 2 for full details)**

Protocol Activity	Screen	Study Day (all activities at 0H [prior to dosing] unless otherwise specified)																			Follow-Up		Early Termination			
		-7	-1	1	2	3-7	8	9-13	14	15-21	22	23-27	28	29	30-35	36	37-41	42	43	44	45	49-56		70-77 a		
Abbreviations used in this table may be found in Appendix 10.																										
Outpatient visit (after ≥8-H fast)	x																							x		
Informed consent	x																									
Adverse event monitoring	x	→	→	→	→	→	→	→	→	→	→	→	→	→	→	→	→	→	→	→	→	x	x	x	x	
Demography and height	x																									
Inpatient stay at CRU		x	→	→	→	→	→	→	→	→	→	→	→	→	→	→	→	→	→	→	x					
Medical history	x	x																								
Review drug, alcohol, tobacco use	x	x																					x			
Review prior/concomitant treatments	x	x																				x	x	x	x	
Review contraception use/requirement	x																				x	x	x	x	x	
Physical examination b	x	x								x											x				x	
Body weight	x	x	x				x		x		x			x						x			x		x	
COVID-19 questionnaire c	x	x																								
COVID-19 testing d	x	x																								
COVID-19 check temperature e	x	x	x	x	x	x	x	x	x	x	x	x	x	x	x	x	x	x	x	x	x	x	x	x	x	
Supine 12-lead ECG f	x				x g		x		x		x			x							x g	x	x	x	x	
Supine vital signs (blood pressure and pulse) h	x				x g		x		x		x			x							x g	x	x	x	x	
Fasting fingerstick blood glucose measurement i		x			x	x	x	x	x	x	x	x	x	x	x	x	x	x	x	x	x	x	x	x	x	
Standardized meals/snacks j		x			x	x	x	x	x	x	x	x	x	x	x	x	x	x	x	x	x	x	x	x	x	
Liquid meal (for MMTT) k																										
IP Administration																										
Blinded IP administration l						x	x	x	x	x	x	x	x	x	x	x	x	x	x	x						
Blood Sampling for:																										
- Safety laboratory tests m	x						x		x														x	x	x	
- FSH, n HIV, HBsAg, HBcAb, HCVAb, HBsAb	x																									
- Free T4, calcitonin, amylase, lipase, HbA1c, TSH, lipids	x																						x			
- Glucose, insulin, C-peptide, m glucagon																										
- PF-07081532 PK					x g		x		x		x			x		x					x o	x o	x o		x	
- 4-β-hydroxycholesterol/cholesterol																										
CCI																										

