**Figure 1. Sample Dosing Scheme**

If a participant does not tolerate dose increment to the next dose level, as determined by the investigator and with notification to the sponsor, the participant may be reverted to the previously tolerated dose level. Following this dose modification, 2 separate attempts at increasing the dose to the next dose level are permitted, per investigator discretion. If, per investigator assessment, unacceptable intolerance (eg, severe vomiting) occurs shortly following dose administration, the dose will not be re-administered on the same day, and the participant may resume dosing at the current dose level at the next scheduled dosing time. Participants whose dose level is tolerability-limited may continue in the study for the intended duration of their assigned cohort at their own individual MTD, as judged to be appropriate by the PI and sponsor.

The planned cohorts in the study (Cohorts 1-3) may be conducted concurrently, partially overlapping or sequentially. The sponsor may decide not to conduct all planned cohorts, if it is judged that study objectives have been met. Up to 3 additional cohorts may be enrolled if judged necessary to meet the study objectives. One or more of the study cohorts may be conducted in non-diabetic participants with obesity, see [Section 4.2.1](#) and [Section 5](#).

Determination of eligibility will occur within 28 days of randomization based on criteria including medical history, vital sign, ECG and laboratory parameters, as detailed in [Section 5](#). Participants deemed eligible will be admitted to the CRU 7 days prior to start of dosing (Day -7) and will remain on-site until at least Day 45, post first dose.

The treatment period with double-blind study intervention will be 42 days, with study drug administered once daily. The participants within a given cohort will be blinded to the study treatment (PF-07081532 versus placebo). Participants who discontinue prior to completion of the study may be replaced, at the discretion of the PI and sponsor.

Upon discharge from the CRU, participants will return to the CRU 7 to 14 days after the last administration of IP for an on-site follow-up visit. A further follow-up contact with participants will be conducted at least 28 days and up to 35 days after the last administration of IP; this contact may be done via a phone call.

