3.3.6. Change from Baseline in Body Weight

Baseline for body weight will be defined as the pre-dose measure on Day 1. The change from baseline and percent change from baseline to all post-dose timepoints as specified in the schedule of activities will be calculated.

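### The follow-up body weight is taken in light clothing but compared with a baseline taken in a hospital gown, so the within-arm change at that visit carries a clothing offset

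*Protocol*

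**What the plan says.** Protocol 8.9.3 (Body Weight) gives separate conditions for the two settings. For outpatient visits it requires an empty bladder and weighing "After removal of shoes, bulky layers of clothing, and jackets so that only light clothing remains". For weights during the stay in the clinical research unit (CRU) it requires a morning measurement before food, drink and dosing, after voiding, and "While wearing only a hospital gown and no shoes".

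SAP 3.3.6 fixes the reference: "Baseline for body weight will be defined as the pre-dose measure on Day 1". It then states: "The change from baseline and percent change from baseline to all post-dose timepoints as specified in the schedule of activities will be calculated". No time point is excluded, and neither document mentions a clothing correction.

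Protocol 4.1 places the visits. Participants are admitted on Day -7 and "will remain on-site until at least Day 45, post first dose". After discharge, "participants will return to the CRU 7 to 14 days after the last administration of IP for an on-site follow-up visit".

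Protocol 9.3.4 plans descriptive statistics for absolute weight, change and percent change, for each treatment on each day. SAP 6.4 contains no body-weight model and no placebo contrast for weight.

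**The concern.** A change from baseline is clean only if both weights are taken the same way. Here every weight from admission to discharge, baseline included, is a gown weight, and the one scheduled weight after discharge is a light-clothing weight. The switch coincides with the end of dosing. A participant whose true weight did not move between the last inpatient weight and follow-up would probably appear to have gained.

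What is at stake is the reading of that single post-treatment time point. Protocol 2.3 expects this drug class to lower body weight, so a step up after the last dose could be taken as partial regain. More participants would not reduce the offset, because it is systematic. Protocol 4.2.4 explains the early admission as a way to cut variability and quantify changes better in parameters that include body weight; changing the weighing condition at follow-up works against that aim.

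**Working it through.** The documents state no clothing weight, gown weight, body-weight SD or target effect, and the sample size is empirical (Protocol 9.5). There is no figure in the plan to reproduce. The check traces the measurement condition through to the planned summary and then applies a simple offset.

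**Step 1: condition at baseline.** SAP 3.3.6 uses Day 1 pre-dose; SAP 3 uses Day -1 as the general default. Both days fall inside the stay that starts on Day -7, so baseline is a gown weight under either definition.

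**Step 2: condition at follow-up.** The visit comes after discharge, 7 to 14 days after the last dose on Day 42: 42 + 7 = 49 and 42 + 14 = 56, which is the Day 49-56 column of Table 1. Protocol 5.3.1 names this visit together with outpatient Screening for the fasting rule. Table 1 also has a row beginning "Outpatient visit (after ≥8-H fast", with a mark at Screening and one late mark. The outpatient weighing rule applies.

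**Step 3: is a weight scheduled there?** The columns of Table 1 are misaligned in the available text. The body-weight row has a mark after the inpatient marks and before the final mark, which is read as Early Termination. The Day 70-77 contact may be a telephone call (Table 1, footnote a), so the mark is best read as Days 49-56.

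**Step 4: offset.** Let *c* = light-clothing weight − gown weight.

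- Observed follow-up change = true change + *c*
- Shift in percent change = 100 × *c* / baseline weight
- Shift in active − placebo (kg) = *c* − *c* = 0, if mean *c* is equal in the arms

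Assumed range for *c*: 0.3 to 1.5 kg. Of the baseline weights below, 50 kg is the entry limit (Protocol 5.1); the others are illustrative.

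| Baseline (kg) | Shift at *c* = 0.3 kg (points) | Shift at *c* = 1.5 kg (points) |
|---|---|---|
| 50 | 100 × 0.3/50 = 0.60 | 100 × 1.5/50 = 3.00 |
| 80 | 0.38 | 1.88 |
| 95 | 0.32 | 1.58 |
| 130 | 0.23 | 1.15 |

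**Step 5: effect by arm.** Suppose true changes of −3 kg on active and −1 kg on placebo, with *c* = 1.0 kg (all assumed). Observed changes are −3 + 1 = −2 kg and −1 + 1 = 0 kg. Each arm's loss is understated by 1 kg, while the difference stays at −2 − 0 = −2 kg.

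For percent change the cancellation is nearly exact. With mean baselines of 90 and 100 kg, the residual is 100 × 1/90 − 100 × 1/100 = 0.11 points.

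**The case against.** The strongest reply is that the comparison between arms survives. Placebo participants are weighed under the same rule, and SAP 6 presents placebo as its own treatment group. Protocol 4.2.4 also foresees placebo-adjusted comparisons in general terms. A reader might infer that the estimated drug effect on weight is biased; the documents do not support that, because the expected offset cancels. Only a within-arm reading is exposed. What weakens the reply is that SAP 6.4 specifies no placebo contrast for weight, and with 3 placebo participants per cohort (9 if the three planned cohorts are pooled) chance differences in clothing add noise.

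A reader might also infer that the shift equals the full weight of the clothes. It does not: a gown has weight too, and only the net difference enters. The upward direction is a reasonable inference rather than a documented fact.

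Third, the importance is limited. The objective concerns weight after multiple doses, which the inpatient weights address under one consistent condition. Persistence after stopping is not an objective. The endpoint is exploratory, nothing is tested (Protocol 9.1), and Protocol 9.3.4 allows exploratory analyses to be left out of the study report. This stands and sets the level of the point.

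Fourth, Early Termination is largely covered. Someone leaving during the stay would be weighed under the inpatient rule; only a weight taken after discharge would not be.

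Finally, feeding state adds little. Protocol 5.3.1 requires a fast of at least 8 hours before the follow-up blood sample, although water is allowed.

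**Conclusion.** The point holds for one quantity: the within-arm change from baseline at the on-site follow-up visit. That change is offset by light clothing minus gown, and no planned step removes it. With a net difference of 0.3 to 1.5 kg, the shift is 0.3 to 1.5 kg, or about 0.3 to 1.6 points at 95 kg. Both the range and the 95 kg are assumptions, and the sign is probably but not certainly upward. If Table 1 in fact schedules no weight at Days 49-56, the point falls away for that visit.

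The active-minus-placebo difference in kilograms is not expected to be biased, and weights from admission to discharge are unaffected. The point is minor. It is worth making because the remedy costs almost nothing.

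**What to change.** **For weights still to be taken.** In Protocol 8.9.3, extend the inpatient conditions (gown, no shoes, voided, before eating and drinking) to the on-site follow-up visit and to any Early Termination weight taken after discharge. With the same condition at both ends, *c* = 0. The cost is one protocol sentence and a change into a gown at a visit that is already fasted and held at the CRU. No visit or procedure is added.

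**For weights already taken.** In SAP 3.3.6 and the matching output, present the follow-up change apart from the inpatient series, footnote the different weighing condition, and interpret it only against placebo. The SAP names no analysis set for body weight, and the PD set as worded requires a dose of PF-07081532, so the summary should use a set that contains the placebo participants.

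**Not recommended.** Screening weight shares the outpatient condition and may look like a ready reference. It predates the Day -7 admission and the assigned-calorie menus (Protocol 4.2.4 and 5.3.1), so a change from screening would mix run-in, diet and confinement with treatment. Screening data used for eligibility also need not be reported (Protocol 9.3.2), and SAP 6 only lists pre-baseline data unless stated otherwise.

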## **9. STATISTICAL CONSIDERATIONS**

Detailed methodology for summary and statistical analyses of the data collected in this study is outlined here and further detailed in a SAP, which will be maintained by the sponsor. The SAP may modify what is outlined in the protocol where appropriate; however, any major modifications of the primary endpoint definitions or their analyses will also be reflected in a protocol amendment.

### **9.1. Statistical Hypotheses**

No formal statistical hypothesis testing will be performed in this study.

### **9.2. Analysis Sets**

For purposes of analysis, the following analysis sets ([Table 4](#)) are defined:

**Table 4. Populations to be Analyzed**

Participant Analysis Set	Description
Enrolled/Randomly assigned to study intervention	"Enrolled" means a participant's, or their legally authorized representative's, agreement to participate in a clinical study following completion of the informed consent process and screening. Potential participants who are screened for the purpose of determining eligibility for the study, but do not participate in the study, are not considered enrolled, unless otherwise specified by the protocol. A participant will be considered enrolled if the informed consent is not withdrawn prior to participating in any study activity after screening.
Full Analysis Set	All participants randomly assigned to study intervention and who take at least 1 dose of study intervention.
Safety Analysis Set	All participants randomly assigned to study intervention and who take at least 1 dose of study intervention. Participants will be analyzed according to the product they actually received.
PK Concentration Set	The PK concentration population is defined as all randomized participants who received at least 1 dose of PF-07081532 and in whom at least 1 plasma concentration value is reported.
PK Parameter Set	The PK parameter population is defined as all randomized participants that received at least 1 dose of PF-07081532 and have at least 1 of the PK parameters of interest calculated.
PD population Set	The PD population set is defined as all randomized participants that received at least 1 dose of PF-07081532 and have at least 1 of the PD parameters of interest calculated.

### 9.3. Statistical Analyses

The SAP will be developed and finalized before any analyses are performed and will describe the analyses and procedures for accounting for missing, unused, and spurious data. This section is a summary of the planned statistical analyses of the primary and secondary endpoints.

#### 9.3.1. General Considerations

#### 9.3.2. Primary Endpoint

All participants who received at least 1 dose of study intervention will be included in the safety analyses and listings. AEs, ECGs, BP, pulse rate, and safety laboratory data will be reviewed and summarized on an ongoing basis during the study to evaluate the safety of

participants. Any clinical laboratory, ECG, BP, and pulse rate abnormalities of potential clinical concern will be described. Safety data will be presented in tabular and/or graphical format and summarized descriptively, where appropriate.

Medical history and physical examination information, as applicable, collected during the course of the study will be considered source data and will not be required to be reported, unless otherwise noted. However, any untoward findings identified on physical and/or neurological examinations conducted during the active collection period will be captured as AEs, if those findings meet the definition of an AE.

Data collected at screening that are used for inclusion/exclusion criteria, such as laboratory data (unless noted below), ECGs, and vital signs, will be considered source data, and will not be required to be reported, unless otherwise noted. Demographic data collected at screening will be reported. In addition, selected screening laboratory data: free T4, HbA1c, TSH, calcitonin, amylase, lipase, TBA and C-peptide will be reported.

### 9.3.2.1. Electrocardiogram Analyses

Changes from baseline for the ECG parameters QT interval, heart rate, QTc interval, PR interval, and QRS complex will be summarized by treatment and time.

The number (%) of participants with maximum postdose QTc values and maximum increases from baseline in the following categories will be tabulated by treatment:

Safety QTc Assessment			
Degree of Prolongation	Mild (msec)	Moderate (msec)	Severe (msec)
Absolute value	>450-480	>480-500	>500
Increase from baseline		30-60	>60

At the nominal time points, the mean of the triplicate measurements will be used to represent a single observation at that time point. If any of the 3 individual ECG tracings has a QTcF value >500 msec, but the mean of the triplicates is not >500 msec, the data from the participant's individual tracing will be described in a safety section of the study report in order to place the >500 msec value in appropriate clinical context. However, values from individual tracings within triplicate measurements that are >500 msec will not be included in the categorical analysis unless the average from the triplicate measurements is also >500 msec.

In addition, an attempt may be made to explore and characterize the relationship between plasma concentration and QT interval length using a PK/PD modeling approach. The results of such analyses will not be included in the CSR.

### 9.3.3. Secondary Endpoints

The populations for PK concentration and PK parameter analyses are defined in [Table 4](#).

PK parameters for PF-07081532 following multiple dose administration will be derived from the concentration-time profiles using non-compartmental methods as data permit. The PK parameters to be assessed in this study, their definition, and method of determination are outlined in Table 5. In all cases, actual PK sampling times will be used in the derivation of PK parameters. PK samples from placebo samples will not be routinely analyzed.

The plasma PK parameters will be summarized descriptively by treatment and day. Each cohort will be considered as a separate treatment. If data permit, dose-normalized area under the plasma concentration time profile from time 0 to 24 hours [AUC24 (dn)] and dose-normalized Cmax [Cmax (dn)] may be plotted against treatment for each day (potentially on a logarithmic scale depending on the extent of the dose range), and will include individual participant values and the geometric means for each treatment. These plots will be used to help understand the relationship between the PK parameters and dose.

Plasma concentrations of PF-07081532 will be listed and descriptively summarized by treatment, day and nominal PK sampling time. Individual participant and median profiles of the plasma concentration-time data will be plotted by treatment and day using actual and nominal times, respectively. Median profiles will be presented on both linear-linear and log-linear scales. Each cohort will be considered as a separate treatment.

**Table 5 Definition of Plasma PK Parameters for PF-07081532**

Parameter	Day 1 (D1) or Day 42 (D42)	Definition	Method of Determination
C max	D1 and D42	Maximum plasma concentration observed from time zero to 24 hours	Observed directly from data
T max	D1 and D42	Time for C max	Observed directly from data as time of first occurrence
AUC 24	D1 and D42	Area under the plasma concentration-time profile from time zero to time 24 hours	Linear/Log trapezoidal method
t 1/2 a	D42	Terminal half-life	Log e (2)/k el , where k el is the terminal phase rate constant calculated by a linear regression of the log-linear concentration-time curve. Only those data points judged to describe the terminal log-linear decline will be used in the regression.
C max (dn)	D1 and D42	Dose normalized C max	C max /Dose
AUC 24 (dn)	D1 and D42	Dose normalized AUC 24	AUC 24 /Dose
C min	D42	Minimum plasma concentration during the dosing interval	Observed directly from data
C av	D42	Average concentration over 24 hours	AUC 24 /24
CL/F a	D42	Apparent clearance	Dose/AUC 24
V Z /F a	D42	Apparent volume of distribution	Dose/(AUC 24 * k el )

**Table 5 Definition of Plasma PK Parameters for PF-07081532**

Parameter	Day 1 (D1) or Day 42 (D42)	Definition	Method of Determination
PTR	D42	Peak-to-trough ratio	$C_{max}/C_{min}$
$R_{ac}$	D42	Observed accumulation ratio for $AUC_{24}$	Steady State $AUC_{24}(dn)/Day 1 AUC_{24}(dn)$
$R_{ac,Cmax}$	D42	Observed accumulation ratio for $C_{max}$	Steady State $C_{max}(dn)/Day 1 C_{max}(dn)$
$AUC_{last}$	D42	Area under the plasma concentration-time profile from time zero to time of last quantifiable concentration	Linear/Log trapezoidal method
$AUC_{inf}^a$	D42	Area under the plasma concentration-time profile from time zero extrapolated to infinite time	$AUC_{last} + (C_{last}^*/k_{el})$ , where $C_{last}^*$ is the predicted plasma concentration at the last quantifiable time point estimated from the log-linear regression analysis and $k_{el}$ is the terminal phase rate constant calculated by a linear regression of the log-linear concentration-time curve. Only those data points judged to describe the terminal log-linear decline will be used in the regression.

a. If data permit

This table includes all PK parameters;  $AUC_{24}$ ,  $C_{max}$ ,  $T_{max}$ ,  $t_{1/2}$  are secondary endpoints, all others are exploratory.

